Tumour sample quality from primary or metastatic tissues was checked, and blood samples were collected at baseline and every 3 months along with abdominopelvic CT scan imaging. The feasibility of bi-weekly cetuximab in combination with chemotherapy (FOLFOX or FOLFIRI) was evaluated by means of progression free survival (PFS), overall survival (OS), objective response rate (ORR), and reported toxicities. The trial hypothesis was that the proposed biomarkers would allow identifying those patients who would benefit the most from bi-weekly cetuximab therapy. KRAS and NRAS mutations were evaluated by pyrosequencing, BRAF and PI3K mutations by RT-qPCR, and PTEN expression by immunohistochemistry. The PFS (time from the signature of the ICF date to PD or death) and OS (time from the signature of the ICF date to death) were analysed and compared between patients with: wild-type (wt) BRAF (wt-BRAF) vs mutant BRAF, and in patients with increased PI3K pathway activation (PI3K mutant or loss of PTEN expression) vs low PI3K pathway activation (wtPI3K and preserved PTEN expression).

Sponsor: Grupo Español Multidisciplinar en Cáncer Digestivo (GEMCAD) Spanish Multidisciplinary Group in Digestive Cancer

Protocol number: GEMCAD 1002 - POSIBA

Clinical Phase: II

Study dates: Study initiation date: first patient enrolled on 27/JUN/2011
Study completion date (last patient completed): 20/JUN/2017

[figure not shown]
This study, including the archiving of essential documents, was performed in compliance with ICH Good Clinical Practice (GCP)

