	
quartiles were calculated according to Brookmeyer and Crowley methods (55,56). Safety data were analysed throughout the entire study.
 
In the first step to develop a prediction model for PFS, univariate Cox regression analysis including all clinical variables collected in the study was performed in order to identify which should be considered for the model selection thereafter in the second step. All factors with a ≤ 0.15 p value (Appendix 15.2, item 4) were selected for the multivariable Cox analysis. The cut-off of ≤ 0.15 p-value was used in order to include the presence of resectable liver metastases as that is a well-known prognostic factor in mCRC. In the second step multivariable Cox regression analysis was performed including those variables identified in the univariate analysis. Importantly, the variable treatment (FOLFIRI vs FOLFOX) was not included for the development of the prediction score because it was not a characteristic intrinsic to the patients.

--	--

12-MONTHS PFS RISK MODEL DEFINITION

Clinical variables and biomarkers were used to build a score to predict 12-months PFS, by using a multivariable Cox regression model built with those clinical variables with a $p \leq 0.15$ in the multivariable analysis (performance status, chemotherapy regimen, sidedness, resectable only liver metastases). Once the first risk score was built adding up the coefficients of the multivariable model ($PS > 0 = 0.6$, left sided = -0.5, resectable liver only metastases = -0.4 and folfiri+cetuximab therapy = Not evaluable), ROC curves were computed for PFS at 12 months using a logistic regression model. All 4 scores (A. Clinical variables including PS, sidedness and resectable only liver metastases, B. Clinical variables + BRAF mutation; C. Clinical variables + PI3K mutation or PTEN ≤ 3 ; D. Clinical variables + DP) had comparable low areas under the curve, ranging between 0.5 and 0.7, overall: The AUC of the score containing the clinical variables was 0.67 (95% CI) (0.60-0.75).

The AUC of the score with clinical variables and BRAF mutational status was 0.68 (0.61-0.75, p-value = 0.37). The AUC of the score with clinical variables and PI3KCA mutation/PTEN status was 0.69 (0.61-0.76, p-value = 0.32). The AUC of the score with clinical variables and DP phenotype was 0.66 (0.58-0.73, p-value = 0.09).

SAFETY RESULTS

CONCLUSIONS

DATE OF THE REPORT:

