4. INTRODUCTION

4.1. COLORECTAL CANCER (CRC)

CRC is the third most common cancer in men (746,000 cases, 10.0% of the total) and the second most common in women (614,000 cases, 9.2% of the total) worldwide. Almost 55% of the cases occur in more developed regions. There is a wide geographical variation in cancer incidence across the world, and the geographical patterns are very similar in men and women; incidence rates vary 10-fold in both sexes worldwide, the highest estimated rates being in Australia/New Zealand (ASR 44.8 and 32.2 per 100,000 in men and women, respectively), and the lowest in Western Africa (4.5 and 3.8 per 100,000).

Mortality is higher (694,000 deaths, 8.5% of the total) with more deaths (52%) in the less developed regions of the world, reflecting a poorer survival in these regions. There is less variability in mortality rates worldwide (6-fold in men and 4-fold in women), with the highest estimated mortality rates in both sexes in Central and Eastern Europe (20.3 per 100,000 for men, 11.7 per 100,000 for women), and the lowest in Western Africa (3.5 per 100,000 for men and 3.0 per 100,000 for women).
http://globocan.iarc.fr/Pages/fact_sheets_cancer.aspx?cancer=colorectal

It is expected that CRC will cause about 50,630 deaths during 2018 in the US. Death rate (the number of deaths per 100,000 people per year) associated with CRC has been dropping in both men and women in the past several decades. One reason for this is that the early diagnosis of colorectal polyps is possible, and these polyps are removed before they can develop into cancers and hinder cancer treatment. In addition, treatment for CRC has improved over the last few decades. As a result, there are now more than 1 million survivors of CRC in the US (1).

According to the Globocan estimation of 2012, 447,136 new cases of CRC were diagnosed in Europe (second most common cancer, accounting for 13.0% of all cancers apart from non-melanoma skin cancers) and 214,866 deaths from CRC in Europe (12.2% of the total number of cancer deaths, second most common cause of cancer-related deaths) (2). The most recent data from REDECAN shows colorectal cancer as the most frequently diagnosed in 2015, followed by prostate (33,370 cases), lung (28,347 cases), breast (27,747 cases), and bladder (21,093 cases) (3)

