PTEN, like BRAF, is another component of the MAPK signalling pathway; therefore, its mutational status may affect cetuximab efficacy. In the study by Laurent–Puig et al. (44), this biomarker was also evaluated. PTEN expression was absent in 19.9% of wt-KRAS patients, and was associated with both PFS and OS. Furthermore, another study (45) evaluated the predictive role of PTEN expression loss in mCRC patients treated with irinotecan+cetuximab. This study demonstrated that the loss of PTEN expression was associated with lower PFS ($p=0.005$).

Consequently, we consider that PTEN expression, along with BRAF, is another biomarker that is worth investigating for the characterisation of the MAPK signalling pathway in this protocol.

Other biomarkers

The list of investigated biomarkers was left open to avoid proposals being outdated; however, based on GEMCAD preclinical studies and recent publications, no other biomarker of interest was identified at the time of database closure.

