6.5 STATISTICAL METHODS PLANNED IN THE PROTOCOL & DETERMINATION OF SAMPLE SIZE

6.5.1 STATISTICAL AND ANALYTICAL PLANS

6.5.1.1. Primary endpoint

To quantify if the biomarkers BRAF, IGF-1RP/MMP-7 (DP), DP and PIK3CA-PTEN improve the prediction of 12-months progression-free survival (PFS) over the use of just clinical variables in the study population we compared the area under the curve (AUC) of a ROC curve using scores composed by clinical variables with the AUC of scores with the clinical variables plus each of the biomarkers.

PFS was defined as the time from the signature of the ICF date to the radiological progression date or death (whatever occurs first). Subjects who had not shown PD and had not died at database closing were censored on the last date of radiological assessment. Subjects who had concluded study treatment before 48 weeks, due to any cause, underwent follow-up every 12 weeks as described in the protocol. Subjects who had undergone metastatic surgery were not censored on the surgery date but were followed up every 12 weeks until progression was documented. Subjects who received other treatment schemas maintaining the same strategy (chemotherapy + monoclonal antibody) without documented PD, were not censored at the time of the change of treatment. Progression to first line for these patients was considered when applicable according RECIST, independently of treatment received. If by any cause, the baseline CT scan was the only imaging evaluation performed (e.g., subject refusal to stay in the study or lost to follow-up), the case was censored on the inclusion date +1 day.

Two groups with a higher and lower likelihood for tumor progression until 12 months were determined based on the designated classification of clinical variables and following proposed biomarker categories :

1. wt-BRAF vs mutant BRAF

2. wtPI3K and PTEN >3 vs mutant PI3K or PTEN ≤3
3. Non-DP vs DP

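### The SAP has no identifiable version date, was written after database closure and prints its primary results, yet it heads as protocol-planned an AUC method and rules that the supplied protocol does not contain.

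*SAP*

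**What the plan says.** **Dates.** The SAP cover shows 27 June 2011 without saying what the date refers to. The signature dates and the report-date field at the end of the synopsis are blank. The title page gives "Study initiation date: first patient enrolled on 27/JUN/2011" and "Study completion date (last patient completed): 20/JUN/2017". SAP 4.1 cites a forecast for 2018: "It is expected that CRC will cause about 50,630 deaths during 2018 in the US". SAP 4.2, on other biomarkers, looks back on the data lock: "no other biomarker of interest was identified at the time of database closure".

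**Results in the plan.** SAP 6.5.1.1 defines the primary analysis as a comparison, for 12-month PFS, of the AUC of a clinical score with the AUC of that score plus each biomarker. The synopsis prints the outcome: coefficients of 0.6, -0.5 and -0.4, four AUCs with intervals, and three p-values. It begins with "The AUC of the score containing the clinical variables was 0.67 (95% CI) (0.60-0.75". Section 7 also prints biomarker group sizes (161/20, 69/98 and 158/23) and counted reasons for stopping treatment.

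**The heading.** Section 6.5, which contains this method, is titled "STATISTICAL METHODS PLANNED IN THE PROTOCOL & DETERMINATION OF SAMPLE SIZE".

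**The protocol.** Protocol 10.2.1 makes the primary endpoint PFS compared between two cohorts defined by a classification. Protocol 10.2.5 bases the sample size on the log-rank method. Protocol 10.4 describes Cox regression and a classification built from the variables with most impact.

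**The concern.** A p-value or AUC carries its usual weight only if the method was fixed before the outcomes were seen. Here a reader has one date, from the start of the trial, and one heading that attributes the methods to the protocol. Taken together they would credit the 12-month AUC comparison and its supporting rules with pre-specification. The supplied protocol does not support that credit, and the text that sets out the rules already contains the answers.

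**Working it through.** **1. Are the printed figures real results?** The AUC of 0.67 cannot be recomputed without patient data, but the width of its interval can be checked.

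- Implied standard error: (0.75 - 0.60)/(2 × 1.96) = 0.038. Since the limits are rounded, the width could be 0.14 to 0.16, giving 0.036 to 0.041.
- Hanley-McNeil: SE² = [A(1-A) + (n₁-1)(a-A²) + (n₂-1)(b-A²)]/(n₁n₂), with a = A/(2-A) and b = 2A²/(1+A).
- With A = 0.67: a = 0.5038, b = 0.5376, A² = 0.4489.
- The SAP gives 181 efficacy patients but not the share with an event by 12 months, so I assume 30% to 70%. At 50% (90 and 91 patients): SE² = [0.2211 + 89 × 0.0549 + 90 × 0.0887]/8190 = 0.00160, so SE = 0.040. Over the whole range SE is 0.040 to 0.046.
- With 87 patients (157 recruited less about 70 without adequate samples) SE would be 0.058 to 0.066.

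The interval fits an analysis of about 181 patients. It is not a placeholder; where the SAP leaves results open, in section 7, it uses X or an empty cell.

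**2. Could the text date from the cover date?** From 27 June 2011 to 20 June 2017 is 2185 days, or 2185/30.4375 = 71.8 months. The completion date, the 221 patients recruited in 47 months (SAP 6.5.2), the 181 analysed and the reference to database closure all come after the cover date.

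**3. Protocol section 10 against the SAP**

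| Item | Supplied protocol | SAP |
|---|---|---|
| Primary comparison | PFS between two cohorts (10.2.1), log-rank basis (10.2.5) | AUC of clinical score against clinical score plus each marker (6.5.1.1) |
| Screening rule | Variables with univariate impact, no threshold (10.4) | p ≤ 0.15 (synopsis, 6.5.1.5) |
| PTEN | No cut-off | Split at 3 (6.5.1.1) |
| Grouping | No rule for forming two groups (10.4) | Cut point taken from the ROC curve (6.5.1.5) |
| PFS start | Date of inclusion (10.2.1) | Date of consent signature (6.5.1.1) |

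The SAP marks none of its entries as post hoc. Its own synopsis says that the log-rank method was the one planned for comparing PFS between the two groups.

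**4. Was any rule set with data in view?** The synopsis says that the 0.15 limit was adopted so that resectable liver metastases would be included, as a known prognostic factor. A threshold can be chosen to admit a named variable only when its p-value is known. The screen is also described inconsistently: univariate in 6.5.1.5, but in the synopsis's risk-model paragraph applied to the multivariable analysis. Chemotherapy regimen is left out of the score in the synopsis and counted among its four clinical factors in 6.5.1.5.

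**5. Size.** Against 0.67, the AUCs with a marker added differ by +0.01 (BRAF, p = 0.37), +0.02 (PI3K/PTEN, p = 0.32) and -0.01 (DP, p = 0.09).

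**The case against.** - **The date.** A reader might infer that the SAP was misdated or backdated. The documents do not show that. The date is unlabelled, equals the study start date and may be meant as such. What stands is that the plan has no identifiable date.
- **A later protocol.** The SAP appears to follow a protocol version that was not supplied: it requires NRAS wild type, names a different tissue laboratory and mentions enrolment up to 240. An amendment could have added the AUC analysis. The finding is therefore limited to the supplied version. However, the SAP as supplied cites no such amendment, and its synopsis still calls log-rank the planned comparison.
- **Openly retrospective text.** The past tense, the 2017 date and a signature statement attesting to conduct and results would alert a careful reader. Dropping the intention-to-treat analysis and changing the sample size are disclosed and explained. This answers any suggestion of concealment, but not the heading of 6.5.
- **The outline was planned.** Protocol 4.4.3, 5.1 and 10.4 foresee a score or classification, a Cox model and the three markers, and 10.4 lets other clinical variables enter on univariate impact. The point therefore concerns the specific rules and the AUC comparison, not the whole approach.
- **The results are null.** A reader might infer that the retrospective choices protect a favourable claim, or that the protocol's analysis would make the conclusion less favourable. Neither is supported. The printed p-values are all above 0.05 and the conclusions section is blank. A log-rank test on groups derived from the same patients could well look more favourable than the AUC comparison.
- **The protocol analysis is not clean either.** Protocol 10.4 has no threshold or cut point, so running it now also needs choices made with the data visible. This stands, and it shapes the fix.

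**Conclusion.** The concern holds in this form: the SAP cannot be dated, it states its primary method together with its results, and it attributes to the protocol a method and rules that section 10 of the supplied version does not contain. All four AUCs (0.66 to 0.69) and the three p-values are affected. At least the 0.15 screen was set by reference to the data; for the PTEN cut, the ROC cut point and the AUC comparison itself, the documents show only that they are absent from the supplied protocol and were written down after closure. The defect is one of provenance and labelling. It does not show that any printed figure is wrong, and it says nothing about intent.

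The conclusion would change for any rule that the sponsor can trace to a protocol version or amendment dated before database lock. The interval check in the working assumes 181 patients and a 30% to 70% event share, and it supports only the statement that the figures are real results.

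The work is the development of a score. The SAP mostly says evaluate; validation is the protocol's word. Coefficients, cut point and AUC all come from the same patients, and SAP 6.5.1.5 describes no separate sample or resampling.

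**What to change.** 1. State the true SAP version date and the database-lock date, and say what 27 June 2011 refers to.
2. Move the coefficients, AUCs, p-values and observed counts from the plan to the report.
3. Change the 6.5 heading. Label as post hoc or exploratory the 12-month AUC comparison and every rule that cannot be traced to a protocol version or amendment dated before lock. Cite the version for each rule that can be traced.
4. Report the protocol's two-cohort PFS comparison (10.2.1, 10.2.5, 10.4) alongside, as the originally planned endpoint. State that its thresholds and cut point were not pre-specified, and that a log-rank p-value on groups derived from the same patients is optimistic unless the derivation is corrected for, for example by cross-validation or bootstrap over all selection steps.
5. Describe the work as score development, not validation.

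Items 1 to 3 and 5 cost only rewording and a check of the amendment file. Item 4 needs one further analysis with resampling on existing data, plus an explicit record of the choices that Protocol 10.4 leaves open. No new patients or measurements are needed.

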3. INVESTIGATORS AND STUDY ADMINISTRATIVE STRUCTURE

4. INTRODUCTION

5. STUDY OBJECTIVES

6. INVESTIGATIONAL PLAN

7. RESULTS

LIST OF ABBREVIATIONS & DEFINITION OF TERMS

Abbreviation/

Acronym Definition

5-FU	5-fluorouracil
AE	Adverse event
AEMPS	Agencia Española de Medicamentos y Productos Sanitarios
ALT	
Alanine aminotransferase	
AST	Aspartate aminotransferase
CEA	Carcinoembryonic antigen
CI	Confidence interval
CNS	Central nervous system
CR	Complete Response
CRF	Case report form
CrCl	Creatinine clearance
CT	Computerised tomography
CTCAE	Common terminology criteria for adverse events
DP	Double-positive
phenotype (Co-expression of p-IGFR-1 and MMP-7)	
DoR	Duration of Response
ECG	Electrocardiogram
ECOG PS	Eastern Cooperative Oncology Group performance status
EGF	Epidermal growth factor
EGFr	Epidermal growth factor receptor
EoT	End of Treatment
FOLFIRI (m)	Chemotherapy regimen with irinotecan and 5-FU/leucovorin infusion
FOLFOX-6 (m)	Chemotherapy regimen with oxaliplatin and 5-FU/leucovorin infusion
GCP	Good Clinical Practice
G-CSF	Granulocyte colony stimulating factor
HIV	Human immunodeficiency virus
ICH	International Conference on Harmonisation
ICF	Informed Consent Form
IGF	Insulin-like growth factor
IGFBP-3	Insulin-like growth factor-binding protein-3
IGFr	Insulin-like growth factor receptor
i.v.	Intravenous
LDH	Lactate dehydrogenase
LLN	Lower limit of normal
ULN	Upper limit of normal
LV	Leucovorin
mAb	Monoclonal antibody
mCRC	Metastatic colorectal cancer
MMP-7	Matrix metalloproteinase- 7
MRI	Magnetic resonance imaging
ORR	Objective response rate
OS	Overall survival
PFS	Progression free survival
PD	Progressive disease
PR	Partial Response
PTEN	Phosphatase & Tensin homolog
RBC	Red blood count
RECIST	Response Evaluation Criteria In Solid Tumours
ROC	
Receiver operating characteristic	
SAE	Serious adverse event
SD	Stable Disease
SEOM	Sociedad Española de Oncología Médica (Spanish Society of Medical Oncology)
SIV	

Site initiation visit

StD Standard Deviation

[figure not shown]
SUSAR Suspected unexpected serious adverse reaction

WBC White blood count

4. INTRODUCTION

4.1. COLORECTAL CANCER (CRC)

CRC is the third most common cancer in men (746,000 cases, 10.0% of the total) and the second most common in women (614,000 cases, 9.2% of the total) worldwide. Almost 55% of the cases occur in more developed regions. There is a wide geographical variation in cancer incidence across the world, and the geographical patterns are very similar in men and women; incidence rates vary 10-fold in both sexes worldwide, the highest estimated rates being in Australia/New Zealand (ASR 44.8 and 32.2 per 100,000 in men and women, respectively), and the lowest in Western Africa (4.5 and 3.8 per 100,000).

Mortality is higher (694,000 deaths, 8.5% of the total) with more deaths (52%) in the less developed regions of the world, reflecting a poorer survival in these regions. There is less variability in mortality rates worldwide (6-fold in men and 4-fold in women), with the highest estimated mortality rates in both sexes in Central and Eastern Europe (20.3 per 100,000 for men, 11.7 per 100,000 for women), and the lowest in Western Africa (3.5 per 100,000 for men and 3.0 per 100,000 for women).
http://globocan.iarc.fr/Pages/fact_sheets_cancer.aspx?cancer=colorectal

It is expected that CRC will cause about 50,630 deaths during 2018 in the US. Death rate (the number of deaths per 100,000 people per year) associated with CRC has been dropping in both men and women in the past several decades. One reason for this is that the early diagnosis of colorectal polyps is possible, and these polyps are removed before they can develop into cancers and hinder cancer treatment. In addition, treatment for CRC has improved over the last few decades. As a result, there are now more than 1 million survivors of CRC in the US (1).

According to the Globocan estimation of 2012, 447,136 new cases of CRC were diagnosed in Europe (second most common cancer, accounting for 13.0% of all cancers apart from non-melanoma skin cancers) and 214,866 deaths from CRC in Europe (12.2% of the total number of cancer deaths, second most common cause of cancer-related deaths) (2). The most recent data from REDECAN shows colorectal cancer as the most frequently diagnosed in 2015, followed by prostate (33,370 cases), lung (28,347 cases), breast (27,747 cases), and bladder (21,093 cases) (3)

Data from the SEOM state that 41,441 new cases of CRC were diagnosed in Spain in 2015 (16.3% of all tumour incidences), making CRC the most diagnosed cancer. Moreover, CRC is the second most common cause of cancer death in our country, after lung cancer, with over 15,449 deaths in 2014 (4).

Out of the newly diagnosed cases, 15–20% correspond to patients with metastatic disease at the time of diagnosis (5) and up to 50% of all patients eventually present with metastatic disease (5,6). Generally, CRC is curable if diagnosed at an early stage, and it is confined to the intestinal mucosa, with a 5-year survival rate of 93% (7). However, the 5-year survival rate decreases to 67% if the tumour spreads to adjacent organs and lymph nodes, and it is only 8% in patients with disseminated metastatic disease (5,7).

4.1.1. CRC treatment

Historically, the median survival rate of patients with metastatic disease has been 11–13 months after treatment with a combination of the fluoropyrimidine, 5-fluorouracil (5-FU), and leucovorin (LV) (8). The introduction of oxaliplatin and irinotecan in advanced colorectal chemotherapy has improved the frequency and extent of clinical response compared with that achieved with 5-FU/LV alone, and it has enhanced progression free survival (PFS) and overall survival (OS). Current research is focused on optimising this systemic chemotherapeutic regimen.

Irinotecan, a specific DNA topoisomerase I inhibitor, has shown significant activity as a single agent in the treatment of patients with CRC refractory to 5-FU (9,10). Furthermore, the addition of irinotecan to the combination therapy with 5-FU/LV (FOLFIRI regimen) significantly improves OS, response rate, and time until progression in the therapy of previously untreated mCRC compared to 5-FU/LV alone (11).

Oxaliplatin, a platinum analogue, causes the inter- and intra-strand cross-linking of DNA, thereby preventing DNA replication. It is effective and well tolerated when administered with LV as a bolus and an infusion (FOLFOX regimen); however, neutropenia and sensory neuropathies are more frequent with this combination than with treatment with 5-FU and LV alone (12,13,14,15,16). In recent years there has been significant progress in the treatment of mCRC, which has resulted in the improvement of patient life expectancy.

Therapies targeted against vascular endothelial growth factor receptor and epidermal growth factor receptor (EGFr) have been recently established in mCRC treatment.

It has been proved that targeted therapies, specifically designed to inhibit carcinogenic biochemical processes, are effective in the treatment of mCRC. Cetuximab (Erbitux®), a chimeric monoclonal antibody targeted against EGFr, has been approved by the FDA for use in combination with irinotecan for the treatment of EGFr-expressing mCRC in patients who are refractory to irinotecan-based chemotherapy. It has also been approved as a single agent for the treatment of EGFr-expressing recurrent mCRC in patients who are intolerant to irinotecan-based chemotherapy (17,18,19,20). Within the European Union (Erbitux® SmPC), cetuximab is indicated for the treatment of EGFr-expressing wt-RAS mCRC:

- in combination with irinotecan-based chemotherapy,
- as first-line therapy in combination with FOLFOX,
- as a single agent in patients refractory to oxaliplatin and irinotecan-based therapy and who are intolerant to irinotecan.

Bevacizumab (Avastin®) is another selective product that binds to and neutralises the biologic activity of human vascular endothelial growth factor-A, a protein with a crucial role in tumour angiogenesis. Bevacizumab, in combination with fluoropyrimidine-based chemotherapy, is indicated for the treatment of mCRC (Avastin® SmPC).

There are 2 monoclonal antibodies targeted against EGFR: panitumumab and cetuximab.

Panitumumab is presently indicated for the treatment of wt-RAS mCRC in adult

patients: • as first-line therapy in combination with FOLFOX or FOLFIRI, • as second-line therapy in combination with FOLFIRI for patients who have received first-line fluoropyrimidine-based chemotherapy (excluding irinotecan), • as monotherapy after the failure of fluoropyrimidine-, oxaliplatin-, and irinotecan containing chemotherapy regimens for the treatment of EGFr-expressing mCRC in patients who are refractory to fluoropyrimidine-, oxaliplatin-, and irinotecan-based chemotherapy (Vectibix® SmPC).

The monoclonal antibody, cetuximab, was approved by the EMEA in July 2008 as first line treatment of mCRC in patients who fulfil the criteria detailed below.

Cetuximab is currently indicated for the treatment of patients with EGFr-expressing wt RAS mCRC:

- in combination with irinotecan-based chemotherapy,
- as first-line therapy in combination with FOLFOX,
- as a single agent in patients who have failed oxaliplatin- and irinotecan-based therapy and who are intolerant to irinotecan (Erbitux® Datasheet).

Therefore, the current indication for cetuximab as first-line treatment in patients with EGFr-expressing wt-RAS mCRC, reflected in the SPC, was established after the CRYSTAL and OPUS clinical trials, and it was verified that cetuximab could be used in routine clinical practice in combination with irinotecan and oxaliplatin chemotherapy regimens as first-line treatment.

The PRIME study results, published in NEJM (Douillard and cols, Sep 2013), showed that patients with mutations of KRAS exon 3 and exon 4 or of NRAS exon 2, exon 3, and exon 4 do not benefit from treatment with FOLFOX and panitumumab compared with FOLFOX alone. The FIRE-3 study, presented at ESMO 2013, confirms the same findings with FOLFIRI+cetuximab vs. FOLFIRI+bevacizumab. Therefore, patients enrolled in this current trial were evaluated for mutational status of the mentioned genes at the indicated exons.

